Table 2 shows elements of the CONSORT diagram for participants in the trial through the first-born offspring's 18th birthday and those available for the 29-year follow-up. Recall that for the postnatal phase of the trial, we followed families assigned to treatments 2 (n=514) and 4 (n=228) for primary assessments. We reviewed medical records on participants for the prenatal phase of the trial, and well-child, emergency-department, and hospital records through child age two. We interviewed participants and conducted tests at intake, 36 weeks of gestation, and child age 6 months, and 1, 2, 4.5, 6, 9, 12 and 18 years of the first-born child's life. At the 18-year follow-up, we completed assessments on 618 mothers and 629 youth, for completion rates of 83% of the mothers and 85% of the children originally randomized, and 86% of the mothers and 90% of the children who had not died prior to the 18-year assessment. Obtaining high rates of sample retention is crucial for ensuring accurate estimates of intervention effect. We will conduct maternal assessments on all cases where the mother had not miscarried, the child had not died in the first two years of life, and the mother had not died or refused by age 18. In the current phase, we will conduct assessments on first-born offspring, irrespective of their mothers' refusal or mortality status. 657 mothers and 687 offspring are available for the year-29 follow-up. Note that we completed an update of participants' current addresses in the spring of 2018. They are displayed at the bottom of Table 2. Among mothers, 84% of those available and found for the 29-year follow-up live in the Memphis metropolitan area, and an additional 3% live within a 3-hour drive of Memphis. Among the 687 offspring available and found, 81% live in the Memphis metropolitan area, and an additional 3% live within a 3-hour drive. It is important to note that all participants in this study received services beyond "usual care." Our experience with mothers and children enrolled in this trial has been that they experience participating in this study as helpful to them, given that health conditions identified in the course of conducting assessments are referred for further evaluation and treatment. We will follow this same procedure in the 29-year follow-up.

Table 2. Sample Recruitment, randomization, attrition, and completed assessments at 18 Years and sample availability for 29-year follow-up

Eligible Subjects Invited to Participate	1289				

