The primary analyses will make use of general linear model methods and their extensions.⁸⁹⁻⁹⁴ The focus will be on (1) full model specification to account for all sources of variation, and full examination of interactions among model factors, including examination of homogeneity of regressions to understand interactions between classification effects and covariates; (2) generalized models to analyze dichotomous outcomes with binomial error distributions and count data assumed to have negative binomial distributions; (3) generalized linear mixed models (including repeated measures and growth-curve models) to account for correlated data and to examine differences in change over time; (4) semiparametric methods to model relations between variables without requiring a specific functional form;⁹⁵ (5) survival analyses including Kaplan-Meier, competing risks and Cox hazard models;⁹⁶⁻⁹⁹ (6) mediation analyses using structural equation models to examine causal processes, including the direct and indirect effects of treatment on outcomes.^{100,101}

The primary classification factors for examination in our models, as determined by our hypotheses and earlier work, include treatments (Control vs. Nurse Visited - T), maternal psychological resources (low versus high based on a median split – P), sex of offspring (S), and follow-up time (A) for outcomes assessed at multiple time points (e.g. obesity) – T|P|S and T|P|S|A. Covariates will be selected using a post-double-selection lasso (least absolute shrinkage and selection operator) procedure.¹⁰²⁻¹⁰⁴ This procedure will select covariates that are most related to intervention status (i.e. differences at randomization) or related to the dependent variable. Candidate covariates will include an index of household poverty, obesity, and maternal

pre-pregnancy BMI.

Statistical Power/Smallest Detectable Differences for Proposed Follow-Up

Given that sample size is fixed, we show below calculations of the smallest detectable treatment-control differences for the 29-year follow-up. Calculations for representative outcomes were carried out with the following assumptions: a Type I error of .05, Type II error of .20 (power of .80), 2-tailed tests, 10 percent of the variance accounted for by other terms in the model for normally distributed variables and N=600. Disproportionate sample sizes in Control and Nurse-Visited groups are taken into account.

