Smallest Detectable Program Effects. Table 6 displays the smallest detectable treatment differences. The study has sufficient power to detect small to moderate effect sizes for normally distributed variables for tests of treatment main effects (.24 SD) and moderate effect sizes (.33 SD) for tests conditioned by a single factor that is evenly distributed between two levels (e.g., offspring sex). For outcomes that are dichotomous, our calculations of smallest detectable treatment differences are calculated in the binomial logistic-linear model and shown for a range of base rates likely to be found in our outcomes. It is important to note that we have detected program effects of this magnitude in earlier phases of the trial and that we have seen that some intervention effects are larger as the mothers and offspring age. We will not make adjustments for multiple comparisons of the primary outcomes (Hypotheses 1-5), but will interpret findings with a critical eye concerning chance effects.

Table 7. Smallest detectable treatment effects for treatment main effects and for subgroups defined by sex

Base Rate for OR	Smallest Detectable Treatment Contrasts for ORs		Smallest Detectable Treatment Contrasts for ORs
	Whole Sample N=600	One Half of Sample (e.g., Mothers of Females) N=300	
10%	.33	.14	
20%	.49	.33	
30%	.55	.42	
40%	.59	.46	
	Smallest Detectable Treatment Contrasts for ESs		Smallest Detectable Treatment Contrasts for ESs
	.24	.33	

Note OR = T_4 odds/ T_2 odds; ES = $(T_4 \text{ mean} - T_2 \text{ mean})/\text{pooled standard deviation}$

Tests of Hypotheses

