Hypotheses 1-6 (primary): The NV group is hypothesized to have: H1: lower measures of obesity, (BMI, waist to hip ratios, segmental and % body fat, visceral fat); H2: lower risks for macrovascular disease, reflected in measures of functional arterial stiffness (peripheral BP, cfPWV, AI); H3: fewer markers of CKD - higher eGFR and lower microalbumin/creatinine ratios; H4: better metabolic outcomes (lower levels of HbA1C, TC, HDL, LDLc, TG, AST/ALT ratio); H5: lower levels of immune/inflammatory markers (hsCRP, fibrinogen, IL-6, TNF-alpha receptor 2, IGF-1); and H6: lower mortality rates. We will test Hypotheses 1-5 by examining each of the primary outcomes listed above as dependent variables in our primary T|P|S model, plus covariates from the post-double-selection lasso results. Outcomes also measured at earlier time points will include an additional classification factor for first-born offspring age at assessment (A). We will examine treatment-control difference summing across levels of maternal psychological resources and sex. In addition, we will examine planned contrasts for males and females, and mothers of males and females. Outcomes for hypotheses 1-5 are normally distributed and will be examined in the general linear model or mixed linear model for repeated measure outcomes. Secondary analyses will examine some outcomes in their dichotomous form for those values that cross clinical thresholds (e.g., obesity), which will be analyzed in the logistic model or generalized linear mixed model for repeated measure outcomes.⁹⁰ Hypothesis 6, related to mortality 6, will be examined in survival analysis by treatment condition without additional classification factors consistent with our earlier report on mortality.^{99,69}

Hypotheses 7: NV effects on H1-5 outcomes will be greater for female offspring and mothers who gave birth to females. Planned contrasts in the above aforementioned models for all primary outcomes, with the exception of mortality (given low base rates), will focus on female offspring and mothers of females.

Hypothesis 8: NV effects on maternal outcomes (H1-6) will be mediated, in part, by NV effects on prenatal health behaviors, preterm delivery in first and subsequent births, and PIH in first births; closely spaced subsequent pregnancies, maternal sense of mastery, stable/supportive partnered

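### The offspring sex-specific contrasts have no safeguard against unequal spread in males and females; over an assumed female/male SD ratio of 0.8 to 1.5, the nominal 5% female test runs at 2.7% to 9.6%

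*Combined protocol and SAP*

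**What the plan says.** The combined protocol and SAP (Tests of Hypotheses, Hypotheses 1-6) fits each H1-H5 outcome in a model crossing treatment (T), maternal psychological resources (P) and offspring sex (S), plus lasso-selected covariates. The outcomes are taken to be normal and "will be examined in the general linear model or mixed linear model for repeated measure outcomes". From that model the plan takes a treatment difference summed over P and S, and then "we will examine planned contrasts for males and females, and mothers of males and females". For H7, the planned contrasts from the same models "will focus on female offspring and mothers of females".

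The sex-specific contrasts are therefore contrasts within one joint fit, not separate fits by sex. Statistical Models and Methods of Analysis promises an examination of interactions and of homogeneity of regressions. The latter concerns slopes, not residual variances. No heterogeneous-variance term, robust standard error or variance diagnostic appears in that section, in Tests of Hypotheses or in Challenges in the Conduct of This Work. Table 7 gives a single detectable standardized effect, .33, for a half sample, scaled by a pooled SD.

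**The concern.** An ordinary general linear model estimates one residual variance and uses it for every contrast. If adult daughters and sons differ in the spread of an outcome, that variance lies between the two true values. It is too small for the more variable sex, whose test becomes anti-conservative, and too large for the other, whose test becomes conservative.

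This matters because the per-sex contrasts are what the plan puts forward for H7. Tables 3 and 4 present earlier sex-specific findings in the same way, as a p-value within one sex with no interaction p-value. H1-H5 carry no multiplicity correction, and the stated protection is coherence across outcomes. Related measures, such as the several adiposity outcomes, could share the same imbalance in spread, so a calibration error could itself look coherent.

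**Working it through.** **Inputs from the documents**
- "a Type I error of .05, Type II error of .20 (power of .80), 2-tailed tests", and "10 percent of the variance accounted for by other terms in the model for normally distributed variables and N=600" (Statistical Power section).
- Allocation: "we followed families assigned to treatments 2 (n=514) and 4 (n=228) for primary assessments". Scaled to N=600 this is 415.6:184.4, and per half sample of 300 it is 207.8:92.2. The plan states that "Disproportionate sample sizes in Control and Nurse-Visited groups are taken into account".
- Sex split 50:50, as the power section assumes. Check: 75% of 1344 recruits is 1008 females; less 657 mothers leaves 351 daughters among 687 offspring, or 51.1%.

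**Assumed input**
- r, the female/male residual SD ratio, is not in the documents. The range used is 0.8 to 1.5.

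**Step 1: the plan's own figures.** Detectable effect = (1.960 + 0.842) × √(1 − 0.10) × √(1/n₁ + 1/n₂).
- N=600: 2.802 × 0.949 × √(1/415.6 + 1/184.4) = 0.235 (plan: .24).
- N=300: 2.802 × 0.949 × √(1/207.8 + 1/92.2) = 0.333 (plan: .33).

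Both reproduce, so the layout used below matches the plan's.

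**Step 2: true error of each contrast under one pooled variance.** Set the male variance to 1 and the female variance to r². With equal sexes the pooled variance is v = (r² + 1)/2. In large samples:
- female error = 2[1 − Φ(1.96 √(v/r²))]
- male error = 2[1 − Φ(1.96 √v)]

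Example, r = 1.25: v = (1.5625 + 1)/2 = 1.28125. Female: 1.96 × √(1.28125/1.5625) = 1.775, giving 0.076. Male: 1.96 × √1.28125 = 2.219, giving 0.027.

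**Step 3: chance of significance in females only.** The two contrasts use different people, so the probability is close to female error × (1 − male error). Half of it falls in the hypothesized direction.

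| r (F/M) | Female error | Male error | Female only | Female only, hypothesized direction |
|---|---|---|---|---|
| 0.8 | 0.027 | 0.076 | 0.025 | 0.012 |
| 1.0 | 0.050 | 0.050 | 0.0475 | 0.024 |
| 1.1 | 0.061 | 0.039 | 0.059 | 0.029 |
| 1.25 | 0.076 | 0.027 | 0.074 | 0.037 |
| 1.5 | 0.096 | 0.0125 | 0.095 | 0.047 |

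Simulation of the eight-cell model at N=600 (40,000 runs per ratio) agrees to within 0.004 throughout. At r = 1.5 it gave 0.096 (female), 0.013 (male) and 0.095 (female only).

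**Step 4: what is not affected.** If K is the allocation factor for one sex, the difference between the female and male contrasts has true variance K(r² + 1) = 2Kv, which is exactly what the pooled model uses. The same holds for their average. Simulated error was 0.049-0.052 for the treatment-by-sex interaction and 0.046-0.051 for the treatment main effect. With 51.1% females the calculated interaction error is 0.048-0.051 over r = 0.8 to 1.5.

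**Step 5: after the change.** With sex-specific variances the simulated error was 0.048-0.051 in females and 0.047-0.051 in males at every ratio tried. Female-only significance was 0.045-0.049. In a separate simulation of 4,000 data sets per ratio, HC3 errors gave 4.4-5.0% at r = 1.3.

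**The case against.** The case against is substantial, and most of it limits the point rather than removing it.

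- **The single variance is inferred.** The documents never say the error variance is pooled. It is the default of the model they name. For outcomes measured at several ages, such as obesity, the plan uses a mixed model whose covariance structure is not stated. The figures above cover only the single-time model.
- **Unequal spread is not shown.** No SD by sex is reported, so neither its presence nor its direction can be established. At r = 0.8 the bias runs against H7.
- **The baseline must be counted.** Female-only significance already occurs 4.75% of the time per outcome with equal SDs. At r = 1.25, the rate in the hypothesized direction moves from 2.4% to 3.7%.
- **H7 says effects are greater in females.** The direct test is treatment by sex, which is in the model and remains calibrated.
- **Scope.** No reason is offered for unequal variance among mothers grouped by their child's sex, and the secondary logistic analyses have no residual variance to pool.

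A reader might infer that the pooled variance manufactures a female-specific programme effect. The documents do not support that: at most it raises the frequency of a pattern that chance already produces, and only for outcomes where females vary more.

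What the objection does not answer is that the plan never names the interaction as the H7 test. It directs attention to the female contrasts, and their p-values and intervals would be reported with no protection against unequal variance.

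**Conclusion.** The point stands as a gap in specification for continuous offspring H1-H5 outcomes. If the general linear model is fitted in its default form and the sexes differ in spread, the planned per-sex contrasts are miscalibrated by the amounts tabulated: modest at a ratio of 1.1, and close to double the nominal female error at 1.5. If males vary more, the female contrast becomes conservative and real female effects are harder to see.

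This rests on three assumptions: a single residual variance (the model's default, not a stated choice), a 50:50 sex split (the plan's own), and an SD ratio that the documents do not supply. The overall treatment effect is not in question, nor is a properly formed treatment-by-sex test with balanced sexes. Nothing here shows that the sex-specific results will be biased toward H7.

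**What to change.** Add to Tests of Hypotheses, for continuous offspring outcomes under H1-H5:

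- Fit residual variances that differ by offspring sex, with covariance specific to sex and age in the repeated-measures models. Alternatively, use HC3 robust standard errors for all planned contrasts.
- Judge H7 by the treatment-by-sex contrast, reported with its interval beside the two per-sex estimates, and not by significance in females alone. The variance change by itself still leaves chance female-only significance at 4.5-4.9% per outcome.

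No new data are needed. The costs are:

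- **If variances are equal:** each per-sex contrast rests on about 300 − 4 = 296 residual degrees of freedom instead of 600 − 8 = 592 (before covariates), which is immaterial.
- **If variances are unequal:** the single .33 SD detectable effect no longer serves both sexes. In pooled-SD units it is 0.333 × r/√v for females and 0.333/√v for males. That gives 0.367 and 0.294 at r = 1.25, and 0.391 and 0.261 at r = 1.5. Table 7 should say so.
- **For H7:** a difference between two per-sex effects has a standard error √2 times larger, so the detectable difference is about 0.333 × 1.414 = 0.47 SD with equal SDs. The plan should state this rather than let the .33 figure stand for H7.

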At the 29-year follow-up, we expect to complete assessments on approximately 80% of those randomized. **Findings from earlier follow-ups have led to our general hypothesis that, over the life-course, the intervention will lead to reductions in the emergence of cardiovascular disease (CVD), chronic kidney disease (CKD), type 2 diabetes (T2D), and premature mortality among both mothers and their first-born offspring.** We will a) conduct anthropometric assessments; b) draw blood to measure cardio-metabolic and immune-inflammatory factors; c) collect random urines to measure the microalbumin/creatinine ratio; d) evaluate arterial stiffness using SphygmoCor Xcel and a standard BP instrument; and e) classify timing and causes of death from National Death Index (NDI) records. To help with interpretation, we will conduct interviews to assess history of diagnoses, medications, menopause, hospitalizations, disability, sedentary and physical activity, sleep, diet, substance use, depression, anxiety, mastery, duration and quality of partnered relationships, education, work, and incarceration; and review hospitalization records, and state records of government-benefits use. We will estimate Nurse-Visited (NV) - Control (C) differences in these outcome domains for both mothers and first-born offspring. Given that previous follow-ups of the Memphis sample for determinations of maternal and offspring mortality have involved all four of the original treatment conditions in this study, we will assess maternal and offspring mortality in all four of those treatment conditions for this phase of follow-up. Moreover, given that maternal mortality due to natural causes will increase as the mothers age, we plan to follow this sample through 2026. The rates of mortality among offspring also will increase over this age-range, so we will assess offspring mortality over the same years. Earlier phases of this study (protocol 04-0518—now closed) examined neighborhood adversity for treatment groups 1 and 3, which involved sending participants' baseline addresses in these groups at the time of registration in this trial to Geolytics, a firm we used to calculate neighborhood adversity scores. Registration in this trial took place in 1989 and 1990. We now wish to include measures of neighborhood adversity in this study for all four treatment groups. Neighborhood adversity can be treated as a baseline factor that may either moderate treatment effects on mortality or account for variance in our estimates of mortality by treatment condition. We now realize the value in obtaining

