Outcome and Age of Assessment	Sample	Comparison	Nurse	Comp vs. Nurse	
Prenatal/Newborn Health		Mean/Rate	Mean/Rat	p-	Effect size*
Pregnancy-Induced Hypertension, % ¹	Whole-T1+2 vs T3+4	20.0	13.0	.009	OR=0.65
Preterm delivery ¹	Whole	13.3	7.3	.020	OR=0.51
Low birthweight, % ¹	LPR ⁸	19.8	9.5	.010	OR=0.42
High birthweight - %	Mothers of F's	5.3	0.0	.005	Not est
Health behavior index, % – 36 wks. ²	Mothers of F's	67.8	80.2	.038	OR=1.18
Inter-Pregnancy Intervals					
Time to first subsequent birth (0-72 mo.) ³	Whole	30.23	34.38	.01	ES=0.26
Count of closely spaced subsequent births–age 0-12 ⁴	Whole	0.51	0.34	.019	IR=0.67
Maternal Economic & Behavioral Resources					
Count of Substances Used – child age 9	Whole	0.17	0.10	.075	IR=0.62
Role Impairment due to Substance Use–ages 9 & 12	Whole	0.25	0.00	.04	Not est.
Sense of mastery – 36 wks preg to 18 yrs ⁵	Whole	99.62	100.95	.009	ES=0.13
% live with partner – across time ⁶	Whole	32.8	36.8	.09	OR=1.20
% married – across time ⁶	Whole	10.7	14.9	.03	OR=1.37
Public Benefits costs (summed-birth-age 18 yrs) ⁷	Whole	\$192,836	\$175,525	.03	ES=-0.13
Maternal Death over 21-year Period after Birth					
All-cause mortality, %	Whole-T1+T2vs T3+4	3.7	1.3	.008	Not Est.
External-cause mortality, %	Whole-T1+T2vs T3+4	1.7	0.2	.02	Not Est.
Measured Maternal Obesity & Hypertension, and Self-Reported Health Problems – through Child Age 18					
Systolic BP – age 18	Mothers of F's	128.85	123.50	.024	ES=0.30
Diastolic BP – age 18	Mothers of F's	90.03	87.02	.044	ES=0.34
Systolic BP – age 12	Mothers of F's	118.40	112.11	.010	ES=0.31
Diastolic BP – age 12	Mothers of F's	82.51	77.73	.010	ES=0.33
Stage 1 Hyperten (Sys \geq 120 or Dias \geq 80) % – age 18	Mothers of F's	84.1	66.3	.002	OR=0.79
Stage 1 Hyperten (Sys \geq 120 or Dias \geq 80) % – age 12	Mothers of F's	63.5	45.8	.025	OR=0.72
Thyroid Problems (self-report), %- age 18	Whole	6.6	2.6	.030	OR=0.38
Kidney Problems (self-report), % - age 18	Whole	2.5	0.5	.037	OR=0.18
Memory problems (self-report) % - age 18	Mothers of F's	2.1	0.0	.038	Not Est.
High Cholesterol (self-report), % - age 18	Whole	8.3	14.4	.023	OR= 1.87

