Figure 1 summarizes how the effects reported in Table 3 are thought to reduce risks for the development of CVD, CKD, and T2D, in mothers. The bold lines show those effects that are established; the lighter lines represent hypothesized relationships; and the dotted lines represent hypothesized relationships between earlier effects and outcomes to be measured in the 29-year follow-up. Program effects on aspects of prenatal health (reductions in PIH, PTD, and LBW) are thought to play a role in reducing maternal hypertension and reported thyroid problems, which in turn will contribute to reductions in measured risks for CVD, T2D, CKD, and mortality in this 29-year follow-up. Note for example that in the control group (T1+T2), 30% of the women who died during the first two decades following birth of the first child had PIH; the corresponding rate among those who died in the T3 nurse-visited condition was 25%, and 14% in the T4 condition. This suggests that part of the reduction in maternal mortality may be explained by or at least correlated with the improvement in conditions for prenatal health that led to PIH in the control group. Moreover, the reduction in short inter-pregnancy intervals is expected to help explain the treatment effect on risks for maternal morbidity and mortality. The reduction in short inter-pregnancy intervals was a major contributor to the reduction in mothers' reliance on public benefits. Intervention effects on economic and social/behavioral resources have implications for the development of chronic disease among mothers, as well as their offspring, especially girls, given that economic adversity is particularly predictive of risks for CVD among females.¹² Note also that the reduction in behavioral dysregulation on the part of nurse-visited children shown in Table 4 below is also likely to play a role in reducing maternal stress, which contributes to inflammation and risk for chronic-disease. We have not attempted full-blown mediation analyses of the inter-relationships among the outcome domains in Figure 1, as the model is complex, with different domains of maternal functioning likely to play a role in both mediating the effect of the program over time and moderating adverse influences on the development of chronic disease.

[figure not shown]

Figure 1. Model of NFP Program Effects on Maternal Risks for Chronic Disease in Memphis Trial

Summary of NFP Effects on Offspring Outcomes in Memphis Trial

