H2: Risks for Macrovascular Disease. We will compare NV and C participants on measures of arterial stiffness: peripheral systolic and diastolic BP (averaged over the two assessments), cfPWV, and AI.

H3: Markers of Chronic Kidney Disease (CKD). We will compare NV and C participants on the estimated Glomerular Filtration Rate (eGFR) and the microalbumin/creatinine ratio.

H4: Metabolic Outcomes: We will compare NV and C participants on measures of Glycosylated Hemoglobin (HbA1C), dyslipidemia (TC, LDL, HDL, TG), and the AST/ALT ratio.

H5: Immune/Inflammatory Markers: We will compare NV and C participants on immune/inflammatory markers [hsCRP, fibrinogen, interleukin 6 (IL-6), tumor necrosis factor alpha-receptor 2 (TNF-2), and insulin-like growth factor-1 (IGF-1 – free and total)].

H6: Mortality. We will compare NV and C participants on rates, ages, and causes of death.

The interpretation of outcomes specified in H1-6 will take into consideration the presence of existing disease and disabilities, based upon interviews, records of medication, diagnoses, and hospitalization records.

Approach to Specific Aim Two (Examine Moderators of Intervention Effects)

As elaborated below, we will examine all outcomes in this study in statistical models that employ sex of offspring as a classification factor and maternal psychological resources cross-classified with Treatment condition (NV-C). We have hypothesized (H7) that intervention effects (H1-5) will be more pronounced among females and mothers who gave birth to females, so analyses of NV-C differences will focus on these groups. We have elaborated methods to address this aim under the statistical methods and models below.

Approach to Specific Aim Three (Explore Mediators of NV Effects)

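### If H6 pools T1+T2 against T3+T4, arms without postnatal follow-up make up 50% of the nurse-visited group but 24% of control; stratifying by follow-up pair is a cheap safeguard

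*Combined protocol and SAP*

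**What the plan says.** H6, lower mortality in the nurse-visited (NV) group, is among the hypotheses labelled primary. Tests of Hypotheses says that it "will be examined in survival analysis by treatment condition without additional classification factors consistent with our earlier report on mortality". The Purpose section notes that previous follow-ups for "determinations of maternal and offspring mortality have involved all four of the original treatment conditions in this study". It plans to use all four again for both generations, and adds that "we plan to follow this sample through 2026".

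The plan does not state which arms form the H6 contrast. For mothers, several places point to pooling:

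- The H6 paragraph under Aim One: "We will compare NV and C participants on rates, ages, and causes of death".
- Statistical Models and Methods of Analysis lists the treatment factor as "treatments (Control vs. Nurse Visited - T", a two-level factor.
- Table 3 labels the earlier maternal mortality rows "Whole-T1+T2vs T3+4".
- The maternal pathways text writes "in the control group (T1+T2), 30% of the women who died during the first two decades".

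Other readings remain open. The Treatment Conditions section uses the word condition for each single arm, so a four-group comparison would also fit. For offspring, the 21-year result is described as T4 against T2.

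Table 1 and the arm descriptions show what differs after birth. T2 and T4 had child developmental screening and referral, followed by assessments through year 18. T1 had nothing postpartum apart from death records. T3 had two postpartum nurse visits, one in hospital and one at home, and otherwise only death records. The section on the retained sample adds that health problems found at assessments are referred for care.

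**The concern.** The four arms cross two factors: nurse visiting (T3, T4 against T1, T2) and postnatal follow-up (T2, T4 against T1, T3). Allocation is unequal between the pairs, 166:230 for T1:T3 and 514:228 for T2:T4. In such a layout a marginal comparison of visited with unvisited women also compares different mixes of follow-up. Randomisation does not prevent this, because the imbalance comes from the allocation ratios. Within each pair the comparison is like for like on follow-up; the pooled unstratified one is not.

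What is at stake is the interpretation of a primary hypothesis. If follow-up lowers mortality, pooling works against visiting: a real benefit is harder to show and an apparent harm more likely. The Data and Safety Monitoring Plan has effects in the unexpected direction logged and reviewed by the monitoring board, so a false signal of harm has consequences. If observed mortality is lower in T1/T3 for any reason, pooling favours visiting.

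**Working it through.** **The plan's own figures.** No event count, hazard ratio or power is given for H6. Table 7 concerns T4 against T2 at N=600 and 300. Its effect sizes reproduce: (1.960+0.842) × √0.9 × √(1/nC+1/nNV) with a 514:228 split gives 0.235 and 0.333, against .24 and .33. They do not bear on deaths.

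**Shares** (arm sizes from Table 1).
- NV: 230/(230+228) = 230/458 = 50.2% from T3.
- Control: 166/(166+514) = 166/680 = 24.4% from T1.
- Live births (Table 2, allocated minus miscarriages and stillbirths: 160, 490, 221, 218): 221/439 = 50.3% and 160/650 = 24.6%.

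**Shift in the pooled ratio with no visiting effect** (all inputs assumed; the documents give none).
- Follow-up lowers mortality by e in T2/T4: [(230+228(1−e))/458] / [(166+514(1−e))/680] = 1.028, 1.061, 1.100 for e = .1, .2, .3.
- National Death Index (NDI) sensitivity s in T1/T3 and .95 in T2/T4: [(230s+228×.95)/458] / [(166s+514×.95)/680] = .986 (s=.9) and .958 (s=.8).
- Both together: .983 (s=.8, e=.1), 1.050 (s=.8, e=.3), 1.013 (s=.9, e=.1), 1.084 (s=.9, e=.3).
- Hazard in T1/T3 at .8 times that in T2/T4, from any cause: .946.

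**Error rates at an assumed 91 deaths** (8% of 1138). SE(log HR) = 1/√(91×.2405) = .214. For e = .3 the shift is .446 SE, and one-sided false-harm error becomes 6.5% instead of 2.5%; for e = .1 it is 3.4%. For s = .8 the shift is −.203 SE, and false-benefit error becomes 3.9%; for s = .9 it is 2.9%.

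**Cost of stratifying** (information proportional to n0·n1/(n0+n1), equal hazards).
- Pooled: 680×458/1138 = 273.67, or .2405 per death.
- Stratified: 166×230/396 + 514×228/742 = 96.41 + 157.94 = 254.35, or .2235 per death.
- Retained: 254.35/273.67 = 93%. SE × √(273.67/254.35) = 1.037.
- Pair weights: 96.41/254.35 = 38% and 157.94/254.35 = 62%.
- With NV hazard ratios of .35 to 1.0 and T1/T3 hazards of .67 to 2.0 times those in T2/T4, SE rises by 2.2% to 4.0%. It rises by 2.6% at about the earlier maternal rates (3.7% vs 1.3%) with no follow-up effect.
- Power at 91 deaths, two-sided .05: 90.0% to 87.8% at HR .50; 79.9% to 76.9% at HR .55. The largest possible loss is 3.2 points (67.9% to 64.7%).

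**Bias against precision.** Stratifying lowers mean squared error when the squared bias exceeds the added variance. At 91 deaths this is 1/(91×.2235) − 1/(91×.2405) = .0035, so |bias| > .059 on the log scale, a pooled ratio outside about .94 to 1.06. Of the nine follow-up and capture scenarios above, two qualify (1.100 and 1.084), one ties (1.061) and six do not. In terms of the T1/T3 to T2/T4 hazard ratio, break-even is about 1.46 at 31 deaths, 1.21 at 120 and 1.13 at 300.

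**Simulation check** (1,500 Cox runs per setting). With no visiting effect and T1/T3 at 1.25 times the hazard, mean log HR was 0.059 pooled and −0.001 stratified. With HR .70 and 1.5 times the hazard it was −0.246 and −0.354, against a true −0.357.

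**The case against.** The strongest case for leaving H6 alone has four parts.

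1. **The contrast is not fixed.** A four-arm comparison, or T4 against T2 for offspring, would not have this problem. This stands: the point is conditional on pooling.
2. **No bias is shown.** The Administrative data section sends identifiers for every enrolled mother and live-born child to the NDI. The section on tracing participants says that attrition bias is minimized for mortality. The T2/T4 screening was developmental screening of the child, and nothing in the documents supports a particular effect on maternal death. This stands too.
3. **Precision.** In most of the assumed scenarios the unstratified estimate has the smaller mean squared error. This is correct. The case for stratifying is that it protects the meaning of a primary contrast at a small, known cost.
4. **Comparability.** Consistency with the earlier report is the plan's stated reason, and changing the estimator once 21-year results are known adds analyst freedom. This is a fair reason to keep the unstratified result in view and to base the change on the design alone. It does not make the pooled groups alike on follow-up.

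A reader might also infer that the separate T4 result in the earlier maternal report was non-significant merely for lack of power. The documents do not settle this: that report rests on about 31 deaths (.037×680 + .013×458), and the text does not name the comparator for T4.

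**Conclusion.** The point holds as a cheap improvement that should be made if H6 uses all four arms as NV against C. The imbalance of 50% against 24% follows directly from Table 1. Its effect on the hazard ratio is unknown. Under the assumed follow-up and capture scenarios the pooled ratio lies between .96 and 1.10 with no true visiting effect.

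Two stronger readings go too far. A reader might infer that the pooled mortality analysis, past or planned, is biased. The documents show neither an effect of follow-up on mortality nor a difference in NDI capture by arm, so they do not support that. A reader might also infer that pooling could create a false benefit only through poorer death capture in T1/T3. In fact any cause of lower observed mortality there would do so.

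Stratifying removes the imbalance in follow-up only. The result still averages prenatal-only visiting (T3 vs T1, 38%) and prenatal-plus-infancy visiting (T4 vs T2, 62%).

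**What to change.** - State the primary H6 contrast separately for mothers and for offspring.
- Where all four arms are used as NV against C, stratify the log-rank test and the Cox model by follow-up pair (T1/T3, T2/T4).
- Show the T4 vs T2 and T3 vs T1 hazard ratios beside the stratified estimate. T4 vs T2 should not replace it on grounds of follow-up alone: it keeps only 157.94/273.67 = 58% of the pooled information.
- Keep the unstratified pooled result as a secondary analysis for comparability with the earlier report.
- Fix and date this wording before the final mortality data are available, giving the allocation ratios as the reason.

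This needs one stratification term, two displayed hazard ratios and a few lines of text, with no new data. The price is about 7% of the information at equal hazards and a primary estimate that is no longer computed exactly as in the earlier report.
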